- Surgery or biopsy to occur at least 12 hours from time of ¹⁸F-DCFPyL dosing but not more than 60 days following ¹⁸F-DCFPyL PET/CT imaging. Imaging used to guide biopsy (e.g., CT, MRI-TRUS, US) will be submitted to the central core imaging lab.
- Follow-up conventional imaging (e.g., targeted MRI/CT, fluciclovine or choline PET) per Investigator's discretion of the anatomical correlate to the lesion(s) identified on ¹⁸F-DCFPyL PET/CT is required in subjects whom evaluable histopathology for prostate cancer is not available. The image(s) will be submitted to the central core imaging lab for review and determination of evaluability.
- If evaluable histopathology result for prostate cancer is not available and follow-up conventional imaging of the PyL-suspected lesion is not informative, subjects initiated on locoregional radiation therapy (RT) alone within 60 days following PyL PET/CT (with no concomitant ADT administered during this time) will be followed every 3 months (± 7 days), up to 9 months post-initiation of RT. PSA response (decline of ≥50% from baseline PSA) must be confirmed (two consecutive levels within 4 weeks) per central lab evaluation.
- Pre-PyL Medical Management Questionnaire (MMQ) will be completed by the treating investigator for all subjects enrolled (who signed informed consent and met all eligibility criteria) in the study prior to Day 1.
- Post-PyL MMQ will be completed by the treating investigator for all subjects who completed ¹⁸F-DCFPyL PET/CT imaging.

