8. ASSESSMENT OF EFFICACY

8.1. Composite Truth Standard

Subjects will undergo Efficacy assessments based on their local PyL PET/CT finding(s) and clinical presentation for evaluation of the composite truth standard, defined either as:

- 1) evaluable local histopathology result for prostate cancer from surgery or biopsy performed within 60 days following PyL PET/CT, or
- 2) if evaluable histopathology is not available, informative conventional imaging (e.g., targeted MRI or CT; fluciclovine or choline PET) finding(s) of the anatomical correlate to the PyL-suspected lesion(s) within 60 days following PyL PET/CT, before locoregional or systemic treatment is started, or
- 3) if neither of the above is available or informative, confirmed PSA response (PSA decline by $\geq 50\%$ from baseline, confirmed within 4 weeks per central lab evaluation) post-RT (no concomitant ADT) that was initiated within 60 days following PyL PET/CT. PSA will be collected every 3 months, up to 9 months until PSA response (if achieved) is confirmed.

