8.5. PSA (total) Response

If evaluable histopathology result for prostate cancer is not available and follow-up conventional imaging of the PyL-suspected lesion is not informative, subjects initiated on locoregional RT

alone (no concomitant ADT within 60 days following PyL PET/CT imaging) will be followed every 3 months for up to an additional 9 months post initiation of RT to assess PSA response to RT alone (without concomitant ADT administered during this time). A blood draw for PSA (total) will be obtained and sent to the central lab at each follow-up assessment. PSA response is defined by decline of $\geq 50\%$ from baseline PSA and must be confirmed within 4 weeks. Subjects will complete follow-up within the 9-month duration once PSA response is confirmed per the central lab.

To be evaluable for PSA response, applicable subjects should undergo RT with fields and target volumes adjusted based on presence of PyL-positive prostate bed, pelvic nodal, visceral or limited osseous metastases.

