The study Schema is in Figure 1 and the Schedule of Assessments is in Table 2

Figure 1: Study Schema

[figure not shown]

Table 2: Schedule of Assessments

	Screening	¹⁸ F-DCFPyL Dosing & Imaging		Safety Phone call ³	Efficacy follow-up ⁴	
Day	-30 to 1	1	1 (60-120 min post-dosing)	8 (±3)	2 to 60	Every 3 months following initiation of locoregional RT, up to 9 months ⁷
Informed Consent & Eligibility	X					
Demographics	X					
Medical History	X					
Prior Medications and Prior Cancer Treatments	X					
Vital Signs (blood pressure, heart rate)		X (pre-dosing)	X			
PSA (Total)	X^1					$X^{1,7}$
Conventional imaging	X^2				X ⁶	
¹⁸ F-DCFPyL Administration		X				
Whole body PyL PET/CT			X			
Surgery or image-guided biopsy & histopathology					X ⁵	
Locoregional radiation therapy per investigator discretion					X ⁷	
Treatment-emergent Adverse Events		Х		X		
Concomitant Medications and Procedures		Х		X	X	X

Statistical Analysis Plan: Protocol PyL3301 October 24, 2019

		Screening	¹⁸ F-DCFPyL Dosing & Imaging		Safety Phone call ³	one Efficacy follow-up	
	Day	-30 to 1	1	1 (60-120 min post-dosing)	8 (±3)	2 to 60	Every 3 months following initiation of locoregional RT, up to 9 months ⁷
Medical Management Questionnaire		X^8				X ⁹	

- 1. Total PSA will be collected and sent to central lab for analysis. If done on Day 1 of Screening, the blood draw should be collected prior to ¹⁸F-DCFPyL dosing.
- 2. Applicable conventional imaging performed as part of standard of care workup within 60 days prior to Day 1.
- 3. A safety phone call will occur 7 (±3) days post-18F-DCFPyL dosing if Efficacy follow-up has not yet occurred.
- 4. Efficacy follow-up visit(s) are only applicable for subjects with positive ¹⁸F-DCFPyL PET/CT finding(s) per local interpretation
- 5. Surgery or biopsy to occur at least 12 hours from time of ¹⁸F-DCFPyL dosing but not more than 60 days following ¹⁸F-DCFPyL PET/CT imaging. Imaging used to guide biopsy (e.g., CT, MRI-TRUS, US) will be submitted to the central core imaging lab.
- 6. Follow-up conventional imaging (e.g., targeted MRI/CT, fluciclovine or choline PET) per Investigator's discretion of the anatomical correlate to the lesion(s) identified on 18F-DCFPyL PET/CT is required in subjects whom evaluable histopathology for prostate cancer is not available. The image(s) will be submitted to the central core imaging lab for review and determination of evaluability.

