- 7. If evaluable histopathology result for prostate cancer is not available and follow-up conventional imaging of the PyL-suspected lesion is not informative, subjects initiated on locoregional radiation therapy (RT) alone within 60 days following PyL PET/CT (with no concomitant ADT administered during this time) will be followed every 3 months (± 7 days), up to 9 months post-initiation of RT. PSA response (decline of ≥50% from baseline PSA) must be confirmed (two consecutive levels within 4 weeks) per central lab evaluation.
- 8. Pre-PyL Medical Management Questionnaire (MMQ) will be completed by the treating investigator for all subjects enrolled (who signed informed consent and met all eligibility criteria) in the study prior to Day 1.
- 9. Post-PyL MMQ will be completed by the treating investigator for all subjects who completed ¹⁸F-DCFPyL PET/CT imaging

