5.1.1. Primary Endpoint

The primary endpoint of the CLR is evaluated in a subset of Full Analysis Set (FAS) subjects with at least one positive lesion identified by ¹⁸F-DCPyL PET/CT imaging by the local reader and then evaluated against the composite truth standard by three independent, blinded central imaging readers. The CLR at the subject level is defined as the percentage of subjects for whom there is a one-to-one correspondence between localization of at least one lesion identified on ¹⁸F-DCFPyL PET/CT imaging (by central review) and the composite truth standard, which is defined either as:

- 1) evaluable local histopathology result for prostate cancer from surgery or biopsy performed within 60 days following PyL PET/CT, or
- 2) if evaluable histopathology is not available, informative conventional imaging (e.g., ¹⁸F-fluciclovine PET (preferred if was not performed at baseline) or choline PET; targeted MRI or CT; fluciclovine or choline PET) finding(s) of the anatomical correlate to the PyL-suspected lesion(s) within 60 days following PyL PET/CT, before locoregional or systemic treatment in is started, or
- 3) if neither of the above is available or informative, confirmed PSA response (PSA decline by ≥50% from baseline, confirmed within 4 weeks per central lab evaluation) post-RT (no concomitant ADT) that was initiated within 60 days following PyL PET/CT. PSA will be collected every 3 months, up to 9 months until PSA response (if achieved) is confirmed.

The CLR in percent is computed as $100 \times TP/(TP+FP)$; TP = true positives, FP = false positives.

A true positive (TP) result is defined as a subject with both a positive lesion(s) on ¹⁸F-DCFPyL PET/CT evaluated by at least one central reader and a positive result on the composite truth standard in the following order of importance:

- Positive finding for prostate cancer of a PyL-suspected lesion according to local histopathology (confirmed by at least one anatomical correlate will suffice to declare the PyL PET/CT assessed by the central reader defining a true positive), or
- Positive finding for prostate cancer of a PyL-suspected lesion upon follow-up correlative imaging by CT, MRI, whole body bone scan, NaF, fluciclovine or choline PET/CT

performed following PyL PET/CT (one confirmed anatomical correlate will suffice to declare the PyL PET/CT assessed by the central reader a true positive), or

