8.6.4. Laboratory Data

Only serum PSA will be assessed in this study. No other laboratory parameters are required. PSA will be an analyzed by a central laboratory. The baseline value is required for all subjects in the safety population and will be presented as descriptive statistics. For those subjects undergoing efficacy follow-up who will undergo radiation therapy, PSA will be evaluated every three months until the baseline value decreases by at least 50%, or until the subject is followed for nine months. For those subjects, the PSA values and changes from baseline will be summarized at each post-treatment visit. The number and percent of subjects who achieve the 50% reduction from baseline at each 3-month follow-up visit will be presented as an efficacy endpoint.

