9.1.4. Visit Windows

The visit windows for each study visit are detailed in Table 7.

Table 7: Visit Windows (Days)

Visit	Relative Target Day	Visit Window (Day)
Screening	-30 to 1	-30 to 1
Study drug dosing and Imaging	1	1
Safety phone call	8	5 to 11
Efficacy follow-up (surgery, biopsy or conventional imaging)	2 to 60	2 to 60
PSA month 3 (locoregional RT)	3 months ±7 days after start of RT, which can be on days 2 to 60	85 to 157
PSA month 6 (locoregional RT)	6 months ±7 days after start of RT, which can be on days 2 to 60	115 to 187
PSA month 9 (locoregional RT)	9 months ±7 days after start of RT, which can be on days 2 to 60	145 to 217

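### The PSA-confirmation rules contradict each other, no visit is set for the confirming draw, and a response first seen at month 9 drops out while a non-response counts as a false positive

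*SAP*

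**What the plan says.** PSA response after radiotherapy without ADT is the third tier of the composite truth standard. It is used only when histopathology and follow-up conventional imaging give no answer.

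**When PSA sampling stops**
- SAP 8.6.4: "PSA will be evaluated every three months until the baseline value decreases by at least 50" percent, or until nine months of follow-up. Confirmation is not mentioned.
- Protocol 8.1: "PSA will be collected every 3 months, up to 9 months until PSA response (if achieved) is confirmed". SAP 5.1.1 has the same rule: "up to 9 months until PSA response (if achieved) is confirmed".
- Protocol 8.5: "Subjects will complete follow-up within the 9-month duration once PSA response is confirmed per the central lab".

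**What confirmation means**
- Protocol Table 3, footnote 7: "PSA response (decline of ≥50% from baseline PSA) must be confirmed (two consecutive levels within 4 weeks) per central lab evaluation". SAP Table 2, footnote 7 repeats it.

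**What is scheduled**
- The only post-radiotherapy PSA column in SAP Table 2 reads "Every 3 months following initiation of locoregional RT, up to 9 months". Protocol Table 3 has the same column.
- SAP Table 7 lists PSA months 3, 6 and 9 only. Its last target is "9 months ±7 days after start of RT, which can be on days 2 to 60".

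**How the result is classified**
- SAP Table 4: a confirmed fall at or before 9 months is TP, an observed but unconfirmed fall is Unevaluable, and no fall with PSA available is FP.
- The PSA bullets for a true positive in Protocol 10.4.2.1 and SAP 5.1.1 require the fall but do not mention confirmation.

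**The concern.** The same PSA history can lead to different samples, and to a different primary-endpoint status, depending on which paragraph is followed. A site working from SAP 8.6.4 would stop at the first fall, and the second level that footnote 7 demands would not exist. A programmer working from the TP bullets would count an unconfirmed fall as TP; one working from Table 4 would set it to Unevaluable.

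Month 9 is the sharpest case. A subject with no fall has a definite status (FP) and stays in the denominator. A subject whose fall first appears at that visit needs a second level, but collection has reached its cap. As written, that subject usually leaves both numerator and denominator. Losing responders while keeping non-responders pulls the PSA-tier CLR down.

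**Working it through.** **1. The plan's own figure.** Inputs from Protocol 10.1 and SAP 7.1: CLR 30%, lower 95% limit 20%, normal approximation.

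n = 1.96² × 0.30 × 0.70 / 0.10² = 80.67, rounded up to 81, as stated.

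Success requires a lower limit above 0.20 for at least two of three readers. With 81 evaluable subjects:
- 24/81 = 29.6%, lower limit 19.7%: fails.
- 25/81 = 30.9%, lower limit 20.8%: passes.

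So at least 25 TP are needed, against an expected 81 × 0.30 = 24.3 at the assumed rate.

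**2. Can scheduled draws confirm each other?** Visits are 3 months apart with ±7 days. Taking 3 months as 90 or 91 days, the smallest gap is 90 − 14 = 76 or 91 − 14 = 77 days, against 28 allowed. They cannot, so an extra draw is always needed.

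**3. Month 9.** A visit at the earliest edge of the window leaves 7 days to the nominal 9 months and 14 to the end of the window. A visit on the target day leaves none before the cap. A full 4-week confirmation period never fits.

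**4. Classification side by side.**

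| PSA course after RT | TP/FP bullets, read literally | SAP Table 4 |
|---|---|---|
| Fall at month 3 or 6, repeat confirms | TP | TP |
| Fall first seen at month 9, no repeat in time | TP | Unevaluable |
| Fall seen, repeat does not confirm | TP | Unevaluable (apparently the same row) |
| No fall by month 9 | FP | FP |

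**5. Size of losing responders.** The documents do not say how many subjects reach the PSA tier, so these are assumptions: share s of evaluable subjects judged by PSA, PSA response rate equal to the overall CLR c, and fraction u of responders unconfirmed. Lost TP = n·s·c·u, so

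CLR′ = c(1 − su) / (1 − csu).

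| s | u | c = 30%: CLR′ (lower limit) | c = 60%: CLR′ (lower limit) |
|---|---|---|---|
| any | 0 | 30.0% (20.0%) | 60.0% (49.3%) |
| 5% | 25% | 29.7% (19.8%) | 59.7% (49.0%) |
| 10% | 50% | 28.9% (19.0%) | 58.8% (47.9%) |
| 20% | 50% | 27.8% (17.9%) | 57.4% (46.3%) |
| 30% | 100% | 23.1% (13.5%) | 51.2% (39.2%) |

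The lower limits use 81 less the lost subjects. The last row is an extreme, not an expectation.

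**6. The opposite effect.** Take 25 TP among 81, plus one subject whose repeat fails to confirm. Dropping that subject gives 25/81 = 30.9%; counting the subject as FP gives 25/82 = 30.5%. Excluding failed confirmations raises the CLR.

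**7. A related slip in SAP Table 7.** Its rule, with RT starting on days 2 to 60 and 30-day months, gives:
- Month 3: 2 + 90 − 7 = 85 to 60 + 90 + 7 = 157, as printed.
- Month 6: 175 to 247, printed as 115 to 187.
- Month 9: 265 to 337, printed as 145 to 217.

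The printed ranges move on by 30 days per visit instead of 90. They do not provide a confirmation window.

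**The case against.** SAP 8.6.4 is a laboratory-summary paragraph in the safety section. The texts that define the endpoint and follow-up all run to confirmation, and footnote 7 is attached to the PSA row of the schedule, so a repeat draw is already mandatory. The TP bullets sit under a composite truth standard that itself asks for a confirmed response, so they can be read as inheriting that condition. The Table 4 limit can also be read as applying to the fall, with confirmation to follow. PSA is the last tier, and enrolment runs until the required evaluable number is reached, so an unevaluable subject is replaced. SAP 8.5.2.2 adds multiple-imputation and tipping-point analyses, and SAP 8.5.2.3 tabulates the CLR by truth standard.

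Much of this stands. A reader might infer that PSA responders in general become unevaluable. The documents do not support that: footnote 7 requires the repeat, so losing a month-3 or month-6 responder is a risk if the draw is missed, not a consequence of the plan. A reader might also take 25/81 (pass) becoming 24/80 (lower limit 19.96%, fail) as the expected effect. That starts exactly at the threshold and ignores replacement: at 81 the result could be 24/81 or again 25/81.

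Three things do not fall away. The month-9 reading is at best ambiguous, and Protocol 8.5, which ends follow-up within the 9 months, favours the strict one. Replacement restores the count but not the proportion, because a replacement is judged under the same rule. The sensitivity analyses fit poorly: imputation by baseline-PSA group ignores the fall already observed, the second imputation's listed methods omit PSA, and every tipping-point shift is negative.

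**Conclusion.** The point holds as an internal contradiction with one definite gap. The stop rules conflict, the required confirming draw has no visit or window, and the TP bullets and Table 4 differ on confirmation. Under the 9-month cap, a fall first seen at month 9 has essentially no route to TP, while a month-9 non-response is FP. For late responders that asymmetry lowers the PSA-tier CLR.

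It does not follow that the primary analysis as a whole is biased toward failure, as a reader might conclude. Failed confirmations also appear to be dropped, which works the other way, and the size of the PSA tier is unknown. Net direction and magnitude therefore cannot be fixed from the documents. With 25 of 81 needed, one or two misclassified subjects could matter if the true CLR is near 30%. At 60%, every setting tabulated leaves the lower limit well above 0.20. This should be corrected before database lock, but it does not invalidate the design.

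**What to change.** - Reconcile SAP 8.6.4 with SAP 5.1.1, Protocol 8.1 and 8.5, and footnote 7, so that one rule says when PSA sampling ends.
- Show the already-required confirming central-lab PSA in Protocol Table 3 and SAP Table 2. Give it a window in SAP Table 7 of up to 4 weeks after the first observed fall, and correct the month-6 and month-9 day ranges there.
- In Table 4, let the 9-month limit apply to the first observed fall, with confirmation allowed up to 4 weeks later. Align the 9-month follow-up wording in Protocol 4.1, 4.3.5.1 and 8.5.
- State in Table 4 how a fall whose repeat sample fails to confirm is classified, separately from a fall with no repeat sample.
- Add confirmation to the TP bullets in Protocol 10.4.2.1 and SAP 5.1.1.

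The cost is wording. For subjects whose first fall is at month 9, it adds one blood draw and up to 4 more weeks of follow-up; for earlier responders the draw is one the endpoint already requires.

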8.6.5. Vital Signs

Blood pressure (systolic and diastolic) and heart rate will be measured and recorded prior to study drug dosing and following dosing on study day 1. The recorded values and their respective changes from the pre-dose values will be summarized using descriptive statistics. A subject listing will present the recorded vital signs for each subject.

8.6.6. Physical Examination

Physical examinations are not required in this study. Any relevant physical finding noted at the screening visit will be included in the subject's medical history. Any changes in or new physical findings following study drug administration will be recorded as AEs.

9. DERIVED AND TRANSFORMED DATA

9.1.1. Baseline Age

The subject's age in years will be calculated based on date of informed consent using the following formula:

Age (years) = FLOOR((date of informed consent - date of birth)/365.25)

where the FLOOR function returns the unrounded integer part of the result.

9.1.2. Study Day

If the date of interest occurs on or after the dosing date, then study day will be calculated as (date of interest – date of dosing) + 1. If the date of interest occurs prior to the dosing date, then study day will be calculated as (date of interest – dosing date). There is no study day 0.

9.1.3. Change from Baseline

Change from baseline is calculated as (post-baseline result – baseline result).

Percent change from baseline is calculated as (change from baseline/baseline result * 100).

If either the baseline or the post-baseline result is missing, the change from baseline and/or percentage change from baseline is set to missing.

9.1.4. Visit Windows

The visit windows for each study visit are detailed in Table 7.

Table 7: Visit Windows (Days)

Visit	Relative Target Day	Visit Window (Day)
Screening	-30 to 1	-30 to 1
Study drug dosing and Imaging	1	1
Safety phone call	8	5 to 11
Efficacy follow-up (surgery, biopsy or conventional imaging)	2 to 60	2 to 60
PSA month 3 (locoregional RT)	3 months ±7 days after start of RT, which can be on days 2 to 60	85 to 157
PSA month 6 (locoregional RT)	6 months ±7 days after start of RT, which can be on days 2 to 60	115 to 187
PSA month 9 (locoregional RT)	9 months ±7 days after start of RT, which can be on days 2 to 60	145 to 217

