If an evaluable histopathology result for prostate cancer is not available and follow-up conventional imaging of the PyL-suspected lesion is not informative, subjects initiated on locoregional RT alone (no concomitant ADT) within 60 days following PyL PET/CT imaging will be followed every 3 months (± 7 days) for up to an additional 9 months to assess PSA response to RT alone (without concomitant ADT administered during this time). To be evaluable for PSA response, applicable subjects should undergo RT with fields and target volumes adjusted based on presence of PyL-positive prostate bed, pelvic nodal, visceral or limited osseous metastases.

A blood draw for PSA (total) will be obtained and sent to the central lab at each follow-up assessment. PSA response is defined by decline of $\geq 50\%$ from baseline PSA and must be confirmed within 4 weeks. Subjects will complete follow-up within the 9-month duration once PSA response is confirmed per the central lab.

Concomitant medications and procedures will be collected. See [Section 8](#) Assessment of Efficacy.

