• PSA decreases by ≥50% from baseline following RT (without concomitant ADT) up to nine months following initiation of such treatment if the other two truth standards were not performed or did not provide evaluable results

False positives will be defined as subjects with positive lesion(s) on PyL PET/CT from at least one central reader who has the following negative findings for prostate cancer according to the composite truth standard:

- Negative finding for prostate cancer of a PyL-suspected lesion according to local histopathology, or
- Negative finding for all PyL positive lesion(s) upon follow-up correlative imaging performed following PyL PET/CT, or
- PSA does not decrease by ≥50% from baseline following RT (without concomitant ADT) up to 9 months following initiation of such treatment.

The CLR lesion location(s) will be matched with the CLR lesion location(s) identified by the composite truth standard to determine if colocalization is successful, denoting a true positive (TP) assessment. If a subject has more than one lesion identified by pathology or by correlative imaging, then at least one lesion must be successfully colocalized for the subject to be considered a TP. The anatomic regions and CLR lesion locations matched by laterality (right or left) where applicable are presented in Table 3. The pelvic lymph nodes are grouped together for analysis in alignment with the data collected in the PyL-2301 (OSPREY) study. Within the prostatic region and extra-pelvic lymph nodes, specific CLR lesion location groupings are further modified specific for PET/CT findings based on Prostate Cancer Molecular Imaging Standardized Evaluation (PROMISE)² intended to guide reproducibility, general applicability and clinical relevance.

Table 3: Lesion Locations and Anatomic Regions

Anatomic Region	CLR Lesion Locations
Prostatic	Prostate gland or prostate bed (including seminal vesicles)
Pelvic Lymph Nodes	 Right Pelvic (including Internal Iliac [Hypogastric], External Iliac, Common Iliac, Obturator) Left Pelvic (including Internal Iliac [Hypogastric], External Iliac, Common Iliac, Obturator) Other pelvic (including Rectal/perirectal and Presacral)

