8.3.5. Prior Prostate Cancer Treatments

The subjects' prior treatments for prostate cancer will be summarized including surgical procedures, prior radiation therapies and systemic therapies (medications). Prior medications will

Statistical Analysis Plan: Protocol PyL3301

be coded using the World Health Organization drug dictionary (WHO-DDE Sep 2018). Prior surgical procedures are categorized as radical prostatectomy (RP), RP with pelvic lymph node dissection, pelvic lymph node dissection alone, Trans-urethral resection of prostate (TURP), and other procedures. radiation therapy is categorized as external beam radiation, brachytherapy and other therapies. The sites of radiation are prostate/prostate bed, pelvic non-prostatic lesions, and extra-pelvic lesions. Summaries will be prepared and will present the number and percent of subjects in the safety population who have these respective therapies recorded on their case report forms. Prior medications will be presented by ATC4 class and preferred term. Prior surgical and radiation therapies will be summarized by MedDRA SOC and preferred term. The time from original prostate cancer diagnosis to study entry (date of informed consent) in months will be summarized, as will the time from each reported prior therapy to study start. A month is defined as (difference in dates /365.25*12.). If partial dates(s) if diagnosis or treatments are reported, then a missing day will be set to the 15th of the month and a missing month will be set to July.

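### SAP Table 7: the Month 6 and Month 9 PSA windows contradict the table's own target rule, and no on-schedule Month 9 PSA can fall in the Month 9 window

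*SAP*

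**What the plan says.** SAP Section 9.1.4, Table 7, gives each PSA visit a target rule and a window in study days:

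- Month 3: "3 months ±7 days after start of RT, which can be on days 2 to 60", window 85 to 157.
- Month 6: "6 months ±7 days after start of RT, which can be on days 2 to 60", window 115 to 187.
- Month 9: "9 months ±7 days after start of RT, which can be on days 2 to 60", window 145 to 217.

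The schedule is the same elsewhere. Footnote 7 to the SAP Schedule of Assessments (Section 4) says that these subjects "will be followed every 3 months (± 7 days), up to 9 months post-initiation of RT". Protocol Section 4.3.5.1 says they are "followed every 3 months (± 7 days) for up to an additional 9 months to assess PSA response".

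SAP Section 8.6.4 summarises PSA values and changes at each post-treatment visit. It adds that the number and percent of "subjects who achieve the 50% reduction from baseline at each 3-month follow-up visit will be presented as an efficacy endpoint".

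**The concern.** The three target rules differ only in 3, 6 or 9 months, so the windows should be about 90 days apart. As printed they are 30 days apart. The protocol and the SAP schedule both support the target rule, so the fault lies in the derived window cells and not in the rule.

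The displays in SAP 8.6.4 need each PSA record assigned to a visit. If Table 7 does this as printed, on-schedule Month 9 values have no window, and Month 6 values fall under Month 9, under two visits at once, or nowhere. The windows also overlap, and the SAP has no rule for a PSA that lies in more than one.

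**Working it through.** **Inputs.** Radiotherapy (RT) starts on study day s, with s from 2 to 60 (Table 7). The tolerance is ±7 days (Table 7). Study day 1 is the dosing day (SAP 9.1.2). Let k be the number of days in 3, 6 or 9 months. Table 7 does not state a month length.

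**Formula.** One subject's on-schedule PSA lies on study days s + k − 7 to s + k + 7. Over all permitted RT starts, the pooled window is 2 + k − 7 to 60 + k + 7.

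**Reproducing the table.** With 30-day months:

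| Visit | k | Window from the rule | Printed window | k implied by the printed cells |
|---|---|---|---|---|
| Month 3 | 90 | 85 to 157 | 85 to 157 | 90 |
| Month 6 | 180 | 175 to 247 | 115 to 187 | 120 |
| Month 9 | 270 | 265 to 337 | 145 to 217 | 150 |

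The Month 3 row reproduces exactly, which identifies the method and the 30-day month. For the other rows, both ends give the same implied k: 115 − 2 + 7 = 120 and 187 − 60 − 7 = 120; 145 − 2 + 7 = 150 and 217 − 60 − 7 = 150. The printed cells therefore correspond to 4 and 5 months.

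**Month 9.** The earliest on-schedule PSA is on day 2 + k − 7:

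- 28-day months (k = 252): Day 247.
- 30-day months (k = 270): Day 265.
- Shortest nine calendar months (k = 273): Day 268.
- 365.25/12-day months (k = 274): Day 269.

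All are later than Day 217. For any visit to fit, k could be at most 217 − 2 + 7 = 222 days, a month of 222/9 = 24.7 days. Day 217 is at most 217 − 2 = 215 days after RT start, about 7 months. Reading the cells as days from RT start does not help: 270 ± 7 is 263 to 277, also outside 145 to 217.

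**Month 6 (30-day months).** The visit lies on days s + 173 to s + 187.

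- RT start on days 2 to 30: every on-schedule day lies in the printed Month 9 window (s = 30 gives 203 to 217).
- RT start on day 15 or later: none lies in the printed Month 6 window (s = 15 gives 188 to 202).
- RT start on days 45 to 60: none lies in any printed window (s = 45 gives 218 to 232).

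There are 59 RT start days × 15 visit days = 885 combinations. Of these, 91 fall in the printed Month 6 window, 540 in the printed Month 9 window (including those 91), and 885 − 540 = 345 in none. For Month 9 the count in its own window is 0 of 885. These counts describe the calendar; they are not probabilities, because RT starts need not be spread evenly.

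**Overlaps as printed.** Days 115 to 157 belong to Months 3 and 6, days 145 to 187 to Months 6 and 9, and days 145 to 157 to all three. With RT start on day 32 or later, every on-schedule Month 3 PSA (s + 83 to s + 97) also lies in the Month 6 window.

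**The case against.** The arithmetic is hard to dispute; the case on the other side is about consequence.

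- **Use of the windows.** The documents do not say that records are assigned by the study-day column or that values outside it are dropped, and SAP 8.6.4 does not cite Table 7. If records are assigned by scheduled visit, the displays are unaffected. This stands: the harm is conditional. But Table 7 is where the SAP defines its visit windows, and it names no other method.
- **The rule is already in the row.** A programmer who used the target column would get the right answer. True, but two columns of one row then give different answers, and the SAP does not say which governs.
- **Month 6 is not wholly lost.** With RT start on days 2 to 14, part of the on-schedule range (days 175 to 187) lies in the printed Month 6 window. This stands. Those 91 combinations also lie in the Month 9 window, so their assignment is ambiguous rather than plainly wrong.
- **The reach is small.** PSA is the third-line truth standard. Sampling stops once PSA has fallen by at least 50% (SAP 8.6.4), and follow-up may end early at database lock (Protocol 10.4.2), so Month 9 records should be few. The by-visit 50% reduction is called an efficacy endpoint in SAP 8.6.4 but is not among those defined in SAP 5.1. All of this stands and limits the importance of the point.

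**Conclusion.** The concern holds. The Month 6 and Month 9 cells contradict the target rule in their own rows, and no on-schedule Month 9 PSA can fall in the Month 9 window for any RT start on days 2 to 60. The corrected Month 6 and Month 9 limits rest on the 30-day month inferred from the Month 3 row. The Month 9 conclusion does not: it holds for any month longer than 24.7 days.

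The effect is confined to the by-visit PSA displays in SAP 8.6.4, and only if Table 7 assigns the records. The primary CLR is not directly affected: SAP 5.1.1 counts a PSA response "up to nine months following initiation of such treatment if the other two truth standards were not performed" or gave no evaluable result, and so times it from RT start without reference to Table 7. The documents do not give the expected number of subjects who reach this truth standard. The table should be corrected before database lock, but the point does not threaten the main result.

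**What to change.** Reconcile the Month 6 and Month 9 cells with the table's stated rule, and say whether PSA records are assigned by window or by scheduled visit.

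- **Preferred.** Restate the three PSA rows as days from each subject's RT start, target ±7 days, and state the month length. With 30-day months the windows are days 83–97, 173–187 and 263–277 after RT start. SAP 8.3.5 uses a different convention for time since diagnosis ("A month is defined as (difference in dates /365.25*12"); with that 365.25/12-day month they are about 84–98, 176–190 and 267–281.
- **Minimum.** Keep study days and replace the two cells with 175 to 247 and 265 to 337. These do not overlap each other or 85 to 157. With calendar months (181–184 and 273–276 days) the upper limits would reach 60 + 184 + 7 = 251 and 60 + 276 + 7 = 343.

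The two options are not equivalent. A pooled study-day window is 73 days wide, against 15 days for one subject. With RT start on Day 2, a PSA on Day 337 is 335 days after RT start, 58 days past the limit of 277, yet it lies inside 265 to 337.

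The cost is two cells, or three rows and a sentence, in the SAP. The protocol, the visit schedule and data collection do not change.
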